9.10.2 Secondary Objective Assessment

Data for the secondary objective assessments will be collected through hypoglycemia awareness questionnaires (Gold, Clark and Pedersen-Bjergaard) [25-27], CGM data, and Fear of Hypoglycemia Questionnaire [28]. The questionnaires will be completed by study subjects at the first, second and the last visit of the study.

The questionnaires and CGM data will be used to determine changes in hypoglycemia awareness, severity and duration of hypoglycemia, onset-to-diagnosis/treatment and diagnosis/treatment-to-recovery durations, fear of hypoglycemia, and overall mean blood glucose values in subjects during the intervention period treated with propranolol compared to placebo.

9.11 Safety Measurements

This study will utilize the CTCAE (NCI Common Terminology Criteria for Adverse Events) version 4.0 for AE and SAE reporting. An electronic copy of the CTCAE v.4 can be found at: https://evs.nci.nih.gov/ftp1/CTCAE/CTCAE_4.03_2010-06-14_QuickReference_5x7.pdf

9.11.1 Safety Monitoring

Vital signs, including heart rate and blood pressure, and adverse events will be assessed during the screening and at the beginning and the end of the interventional phase. Physical examination will be conducted and instruction for further medical assessment will be provided if needed. A pregnancy test will be conducted during the screening and before the study drug intervention. The subjects will be provided contact information for questions and needs related to the study.

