4.2 Dose Limiting Toxicity

Propranolol ER will be administered at a dose of 80 mg daily during the Interventional Phase. This dose of propranolol is within the range of other indications that have been approved by FDA previously. If study subjects experience serious adverse events or intolerable toxicities determined by the PI to be related to treatment with propranolol, subjects will be discontinued from the trial, or treatment may be held for one week and resumed if adverse events resolve to a tolerable level as determined by the investigator.

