6 TREATMENT PLAN

6.1 Administration Schedule

6.1.1 Group 1

After randomization and the initial two-week CGM assessment, subjects randomized to Group 1 will be initiated on propranolol ER 80 mg daily (before bedtime) for four weeks, and will then stop the intervention.

6.1.2 Group 2

After randomization randomization and the initial two-week CGM assessment, subjects randomized to Group 2 will be initiated on placebo: one capsule daily (before bedtime) for four weeks, and will then stop the intervention.

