6.2.2 Preparation and Administration

Subjects will be given a 4-week supply of blinded study medication at treatment visit 2. Subjects will be asked to return this supply with any unused capsules at the end of the intervention period.

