6.3 Duration of Therapy

The standard treatment period for the interventional period (propranolol or placebo) will last 4 weeks (28 days).

Subjects must be withdrawn or discontinued from the clinical trial for the following reasons:

- Subject withdraws consent from participation in the clinical trial. A subject must be removed from the study at his/her own request. At any time during the trial and without providing reasons, a subject may decline to participate further. The subject will not suffer any disadvantage as a result.
- Subject is lost to follow-up despite efforts to contact
- Death

Subjects may be withdrawn or discontinued from the clinical trial for the following reasons:

- The subject is non-compliant with study treatment requirements and/or protocol procedures, including the use of prohibited concomitant medications.
- The occurrence of an AE, laboratory abnormality, or other medical condition or situation such that in the investigator's opinion, continued participation in the study would not be in the best interest of the subject.
- Development of severe hypoglycemia for which subject was required to visit emergency room or to be hospitalized

Discontinued or withdrawn subjects may be replaced on study to ensure completion of five study subjects in each treatment arm.

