7 TOXICITIES AND DOSE MODIFICATION

Toxicities will be monitored in each study subject according to the study calendar and Section 9.9, Safety Measurements. Serious Adverse Events and intolerable toxicities determined by the PI to be related to study medication will result in discontinuation of treatment and withdrawal of the subject from the trial, or treatment may be held for one week and resumed if adverse events resolve to a tolerable level as determined by the investigator.

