8 STUDY CALENDAR

Period	Screening ¹	Study ²			
		Intervention Phase			
Visit No.		1	2	3	4
Week	-4 to 1	1	3	5	7
Assessments					
Informed consent	X				
Inclusion/Exclusion criteria	X				
Demographics	X				
Vital signs	X		X		X
Physical Examination	X		X ³	X ³	X ³
Hemoglobin A1C	X				
Pregnancy Test	X		X		
ECG	X				
AE Assessment			X	X	X
Concomitant Medications			X		X
Investigational Drug Treatment			X		
Primary Objective Assessment		X ⁴		X ⁴	
Secondary Objective Assessment		X	X		X

ECG, electrocardiogram; AE, adverse event

1. All screening procedures should be completed within 4 weeks of study enrollment, except that an ECG completed within 3 months will be considered as valid. Screening visit and Study Visit 1 may occur on the same day.
2. All visits within the Intervention Phase should occur within ± 3 days of the target dates. Pregnancy test which must be completed within 48 hours before investigational drug treatment starts.
3. Physical exam to be conducted at the discretion of PI/Sub-investigator based on reported adverse events.
4. Two-week assessment with Hypoglycemia Event Reports and continuous glucose monitoring.

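### After the pre-dose Visit 2 reading, no pulse or blood pressure is scheduled until Visit 4 (nominal day 28 of 28), so a symptomless fall could go unseen until treatment is over or nearly over

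*Combined protocol and SAP*

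**What the plan says.** For vital signs, the text and the calendar are consistent. Section 9.11.1 asks for heart rate and blood pressure at screening and "at the beginning and the end of the interventional phase". The Section 8 calendar marks them at Screening, Visit 2 (week 3) and Visit 4 (week 7), and leaves Visit 3 (week 5) blank. Section 9.7 lists what is measured but adds no time points. The ECG is done at screening only (9.8).

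On the start of treatment, Section 6.2.2 says: "Subjects will be given a 4-week supply of blinded study medication at treatment visit 2". Section 6.1 has the active arm "initiated on propranolol ER 80 mg daily (before bedtime) for four weeks"; placebo follows the same timing. Section 6.3 gives the treatment period as 28 days. On visit timing, calendar footnote 2 says: "All visits within the Intervention Phase should occur within ± 3 days of the target dates".

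Visit 3 does have an adverse-event assessment. Any examination there follows footnote 3: "Physical exam to be conducted at the discretion of PI/Sub-investigator based on reported adverse events". Section 9.11.2 relies on non-directive questioning at visits and on events that subjects volunteer during or between visits.

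On action, Section 6.3 allows withdrawal for "The occurrence of an AE, laboratory abnormality, or other medical condition or situation" where the investigator thinks continuing is not in the subject's interest. Section 4.2 allows discontinuation or a one-week hold for "serious adverse events or intolerable toxicities determined by the PI to be related to treatment with propranolol", and Section 7 repeats this. Section 7 also says: "Toxicities will be monitored in each study subject according to the study calendar".

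**The concern.** Section 3 lists bradycardia, intensified atrioventricular block and hypotension among the reported effects of propranolol. A fall in pulse or pressure can be clinically significant without the subject feeling anything. Open questioning would not bring it out, and an examination prompted by a reported event would not be prompted. Under 9.11.2 an abnormal test result counts as an adverse event if it is considered clinically significant, but nobody can make that judgement without a reading. Because Section 7 ties toxicity monitoring to the calendar, a blank in the calendar is a gap in the planned monitoring, although nothing forbids an unscheduled measurement.

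What is at stake is the timing of the investigator's decision. The power to withdraw a subject is most useful while doses remain, and at the first scheduled reading after drug start there are nominally none left. The gap is confined to symptomless changes.

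**Working it through.** **Inputs.** Target weeks: Visit 2 = 3, Visit 3 = 5, Visit 4 = 7 (Section 8). Window ±3 days per visit (Section 8, footnote 2). One dose nightly before bedtime, starting after Visit 2 (6.1, 6.2.2). Planned length 28 days, so 28 doses (6.3). Twelve subjects (4.3).

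**The plan's own figure.** Visit 2 to Visit 4 = (7 − 3) × 7 = 28 days, which matches the 28-day treatment period.

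**Is Visit 2 an on-treatment reading?** No. The supply is given at that visit and the first dose is taken at bedtime, so the reading is pre-dose.

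**Intervals.** Take Visit 2 as day 0.
- Visit 2 to Visit 4: 28 days. With each visit moving by up to 3 days in opposite directions, 28 − 6 = 22 to 28 + 6 = 34.
- Visit 2 to Visit 3: (5 − 3) × 7 = 14 days, range 14 − 6 = 8 to 14 + 6 = 20.
- Visit 3 to Visit 4: likewise 14 days, range 8 to 20.

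**Doses.** At a visit on day d, doses taken = min(d, 28) and doses that withdrawal could still avoid = 28 − min(d, 28).

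| First reading after drug start | Day: nominal (range) | Doses taken | Share of 28 | Doses left |
|---|---|---|---|---|
| Visit 4 (as planned) | 28 (22 to 34) | 28 (22 to 28) | 100% (79% to 100%) | 0 (0 to 6) |
| Visit 3 (if added) | 14 (8 to 20) | 14 (8 to 20) | 50% (29% to 71%) | 14 (8 to 20) |

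At the late end of the window, Visit 4 comes 34 − 28 = 6 days after treatment was due to end. A reading taken then is no longer an on-treatment reading.

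**Longest scheduled interval between readings, from Visit 2 onward.** Now 28 days (at most 34); with a Visit 3 reading, 14 days (at most 20). The interval from Screening to Visit 2 does not change. Screening may precede enrolment by up to 4 weeks; if enrolment is taken as Visit 1, that interval can reach 28 + 14 = 42 days before windows.

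**Sensitivity.** If the windows are instead counted from the actual first dose, Visit 4 falls on day 25 to 31 with 0 to 3 doses left, and Visit 3 on day 11 to 17 with 11 to 17 doses left. The conclusion is the same.

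**The case against.** The strongest case against has three parts.

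*The schedule is a coherent choice and the remaining gap is narrow.* This stands. No objective or rule fails. Section 3 describes the dose as the lowest, exposure is four weeks, and subjects with cardiovascular disease, conduction abnormality, heart failure or a contraindication to beta-blockers are excluded (5.2). Everyone has a screening ECG. Symptomatic events are picked up by the Visit 3 assessment, by volunteered reports and through the contact details subjects receive. These points limit the importance of the gap but do not supply a reading.

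*The route to action is thin.* This stands in part. Sections 4.2 and 7 require a related event that is serious or intolerable, and a symptomless change would seldom be intolerable. In practice the discretionary clause in 6.3 is the main route. The count of doses left is therefore an opportunity to stop, not a measure of harm averted.

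*A Visit 3 reading could affect blinding.* This also stands. Visit 3 opens the on-treatment diary and CGM period (Section 8, footnote 4), and the primary outcome has self-reported events in its numerator (9.10.1). A lowered pulse seen there could hint at allocation, whereas Visit 4 falls when the diaries are collected. Withholding the value from the subject reduces this risk but does not remove it.

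A reader might also infer more than the documents support. They do not show that on-treatment safety monitoring is absent, because reported events are covered. Nor do they show that holding and resuming treatment is impossible: the hold remains usable for reported events, and the protocol does not say whether it extends the 28 days.

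**Conclusion.** The point holds as a minor one. After the pre-dose reading at Visit 2, the next scheduled pulse and blood pressure come nominally when all planned doses have been taken, and at the earliest when 79% have. A clinically significant but symptomless fall could go unseen for that time.

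This rests on three assumptions: the windows at each visit move independently, no doses are missed or held, and dosing starts on the night of Visit 2. The documents give no rate for such events, so no frequency or size of harm is claimed, and it would be wrong to read the point as evidence that subjects face a substantial known risk. Nor does the gap bias the primary analysis, which uses diary and CGM events and not vital signs. The change is worth making because it is inexpensive and uses an existing visit; it is not a condition for the trial to proceed.

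**What to change.** Mark vital signs at Visit 3 in the Section 8 calendar and add one sentence to 9.11.1: *Heart rate and blood pressure will also be measured at Visit 3; values will not be disclosed to the subject unless clinically needed.*

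Leave the adverse-event wording as it is. No threshold, stopping rule or separate staff is needed; action on a reading stays with the investigator, chiefly under 6.3.

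Cost: one reading per subject, so 12 in all, and more if withdrawn subjects are replaced. At an assumed 5 to 10 minutes each, that is 12 × 5 = 60 to 12 × 10 = 120 minutes, or 1 to 2 hours over the whole study. The change is a minor amendment and needs IRB approval before use (12.1). The small blinding risk described above remains.

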9.11.2 Adverse Events

An adverse event is the appearance or worsening of any undesirable sign, symptom, or medical condition occurring after starting the study drug even if the event is not considered to be related to study drug. For the purposes of this study, the terms toxicity and adverse event are used interchangeably. Medical conditions/diseases present before starting study drug are only considered adverse events if they worsen after starting study drug. Abnormal laboratory values or test results constitute adverse events only if they induce clinical signs or symptoms, are considered clinically significant, or require therapy.

Collection of adverse events will begin following the initial treatment with propranolol and placebo and continue through the last treatment visit. Adverse events will be documented in the study source record and recorded in the CRF.

Information about all adverse events, whether volunteered by the subject, discovered by investigator questioning, or detected through physical examination, laboratory test or other means, will be collected and recorded and followed as appropriate.

The occurrence of adverse events should be sought by non-directive questioning of the patient at each visit during the study. Adverse events also may be detected when they are volunteered by the patient during or between visits or through physical examination, laboratory test, or other assessments. As far as possible, each adverse event should be evaluated to determine:

1. The severity grade based on CTCAE v.4
2. The relationship of the event to the study drug(s): definite, probable, possible, unlikely, not related.
3. The duration: start and end dates, or continuing at final follow-up visit
4. Action taken: (e.g. study drug interrupted or dosage modified, concomitant medication taken, non-drug therapy, hospitalization, or no action taken)
5. Whether the event constitutes a Serious Adverse Event (SAE)

All adverse events will be treated appropriately. Such treatment may include changes in study drug treatment as listed in the dose modification section of this protocol. Once an adverse event is detected, it should be followed until its resolution, and assessment should be made at each visit (or more frequently, if necessary) of any changes in severity, the suspected relationship to the study drug, the interventions required to treat it, and the outcome.

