3 DRUG INFORMATION

Propranolol (investigational drug) has been approved by FDA for indications unrelated to the current study. [24] In the current study, we will use Propranolol extended release (ER). A summary of the FDA label for propranolol has been provided in the following.

Propranolol hydrochloride is a stable, white, crystalline solid which is readily soluble in water and ethanol. Its molecular weight is 295.80. Propranolol hydrochloride extended-release capsules are formulated to provide a sustained release of propranolol hydrochloride.

Propranolol is highly lipophilic and almost completely absorbed after oral administration. However, it undergoes high first pass metabolism by the liver and on average, only about 25% of propranolol reaches the systemic circulation.

Approximately 90% of circulating propranolol is bound to plasma proteins (albumin and alpha-1-acid glycoprotein). The binding is enantiomer-selective. The S(-)-enantiomer is preferentially bound to alpha-1-glycoprotein and the R(+)-enantiomer preferentially bound to albumin. The volume of distribution of propranolol is approximately 4 liters/kg. Propranolol crosses the blood-brain barrier and the placenta, and is distributed into breast milk. Propranolol is extensively metabolized with most metabolites appearing in the urine.

Propranolol is indicated for hypertension, angina pectoris due to coronary atherosclerosis, migraine and hypertrophic subaortic stenosis.

Propranolol is contraindicated in 1) cardiogenic shock; 2) sinus bradycardia and greater than first-degree block; 3) bronchial asthma; and 4) in patients with known hypersensitivity to propranolol hydrochloride.

There have been reports of exacerbation of angina and, in some cases, myocardial infarction, following abrupt discontinuance of propranolol therapy. Therefore, when discontinuance of

propranolol is planned, the dosage should be gradually reduced over at least a few weeks, and the patient should be cautioned against interruption or cessation of therapy without the physician's advice. Since this study will be using the lowest dose of propranolol LA, and the age of the tested population imposes a lower risk of significant atherosclerotic disease, the dose will not be tapered.

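### Adverse-event collection stops at Visit 4, on target 0–1 day after the last untapered dose, and no later safety contact is scheduled

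*Combined protocol and SAP*

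**What the plan says.** Section 9.11.2 starts adverse-event collection at the first dose and has it "continue through the last treatment visit". It gives no visit number. The Study Calendar (Section 8) places its last adverse-event assessment at Visit 4, week 7, and has no later column. Section 9.11.1 agrees: its last assessment is at the end of the interventional phase. A calendar footnote adds: "All visits within the Intervention Phase should occur within ± 3 days of the target dates".

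On stopping the drug, Section 3 notes reports of "exacerbation of angina and, in some cases, myocardial infarction, following abrupt discontinuance of propranolol therapy" and says that, when stopping is planned, "the dosage should be gradually reduced over at least a few weeks". It then says that in this study "the dose will not be tapered", because the dose is the lowest available and the age range carries less atherosclerotic risk.

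Some provisions do reach past Visit 4:

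- Section 9.11.1: "The subjects will be provided contact information for questions and needs related to the study".
- Section 9.11.2: "Once an adverse event is detected, it should be followed until its resolution".
- Section 9.11.3 requires all serious adverse events to be recorded and sets no end date.
- Section 9.11.5 has a dated rule (30 days), for pregnancy and lactation only.

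Item 3 in 9.11.2 allows an event to be recorded as "continuing at final follow-up visit", and Section 4.5 gives three months of participation. Neither defines a contact after Visit 4.

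**The concern.** The protocol identifies a hazard of abrupt withdrawal, chooses abrupt withdrawal, and then ends active safety questioning at about the moment the drug is withdrawn. Visit 4 is a real safety contact, with an adverse-event assessment and vital signs, but on target it sees almost no time off drug.

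Two things are at stake. The first is the individual subject: nobody is scheduled to ask how subjects fared after stopping. The second is ascertainment: the adverse-event review after every sixth completer (Section 12.2) would have little actively collected information from after withdrawal. Section 10 says that the full-scale trial will be a cross-over. By inference, subjects given propranolol first would stop it part-way through that trial, so experience after stopping is useful for planning.

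**Working it through.** **Inputs.** Visit 2 is in week 3 and Visit 4 in week 7, each ±3 days (Section 8). A 4-week supply is dispensed at Visit 2 (6.2.2). Dosing is once daily at bedtime (6.1) for 28 days (6.3). Twelve subjects enter two arms (4.3, 4.1), and replacement aims at five completers per arm (6.3).

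**Check of the plan's own figure.** Take week w to start on day 7(w − 1) + 1. Visit 2 is then day 15 and Visit 4 is day 43. The interval is 43 − 15 = 28 days, which matches the stated treatment period.

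**Last dose to Visit 4, for 28 consecutive doses.** The last dose falls 27 days after the first.

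- On target, first dose on the evening of Visit 2: last dose on day 15 + 27 = 42, so the gap is 43 − 42 = 1 day.
- On target, first dose a day later: 43 − 43 = 0 days.
- Longest, with Visit 2 at −3 (day 12) and Visit 4 at +3 (day 46): last dose on day 39, gap 46 − 39 = 7 days.
- Shortest, with Visit 2 at +3 (day 18) and Visit 4 at −3 (day 40): planned last dose on day 45, so Visit 4 comes 5 days before it, or 6 days if dosing began the day after Visit 2. Essentially no time off drug is then observed.

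Two kinds of subject fall outside this range. One who stops early but still attends Visit 4 can have a gap above 7 days. One whose treatment is held for a week (4.2, Section 7) and who then finishes the supply, which the protocol neither requires nor rules out, takes the last dose on day 42 + 7 = 49, 6 days after an on-target Visit 4.

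**What a call adds.** A call k days after the last dose extends observation, by recall, by k minus the gap. For gaps of 0–7 days, a 2-week call adds 7–14 days and a 3-week call adds 14–21.

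**What so few subjects can show.** With zero events in n subjects, the one-sided 95% upper limit is 1 − 0.05^(1/n): 39% for n = 6 and 45% for n = 5. The chance of seeing at least one event is 1 − (1 − p)^n:

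| Assumed rate p | n = 6 | n = 5 |
|---|---|---|
| 1% | 6% | 5% |
| 5% | 26% | 23% |
| 10% | 47% | 41% |
| 20% | 74% | 67% |

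Six per arm assumes that the 12 subjects split equally. The rates are illustrative.

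**Fit with Section 4.5.** Take three months as 91 days and allow the full 28 days of screening. An on-target last dose on day 42 is 41 days after day 1.

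- 3-week call: 28 + 41 + 21 = 90 days on target, and 93 if Visit 2 is at +3.
- 2-week call: 28 + 41 + 14 = 83 days on target, and 86 if Visit 2 is at +3.

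**The case against.** The strongest reply is that the hazard is already largely handled. The dose is low, age is capped at 59, Section 5.2 excludes major cardiovascular disease, conduction abnormality and heart failure, and an ECG is done at screening. An infarction would be a serious adverse event, and 9.11.3 has no cut-off. Subjects hold contact details, and detected events, including those that lead to withdrawal, are followed to resolution. What remains is active questioning for new and mostly non-serious events, with small expected yield.

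Most of this stands, and it is why the point is modest. It does not close the gap. Follow-up to resolution needs an event that has already been detected. Contact details and open-ended serious-event recording work only if the site hears of the event. The reasons in Section 3 support not tapering; they do not bear on when to stop asking.

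It can also be said that the undefined follow-up visit and the three months of participation show that a later contact is intended. That is possible, and the study schema figure cannot be seen here. But the calendar is intact and has no such contact, so a site following it would make none.

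Three stronger readings are tempting, and the documents support none of them:

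- **The untapered stop is unsafe, or events will be missed at some known rate.** No onset time or rate for withdrawal events is given.
- **The 30 days in 9.11.5 measure the share of risk left unobserved.** That is a pregnancy and lactation reporting window and says nothing about when withdrawal events occur. Likewise, the few weeks in Section 3 are the length of a taper.
- **A follow-up call would test the no-taper decision.** Five or six treated subjects cannot do that.

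**Conclusion.** The point holds as a change that should be made, though nothing here prevents the trial from proceeding. Followed exactly, the collection rule ends active questioning 0–1 day after the last dose on target, and at most 7 days after it for a subject who takes 28 consecutive doses within the windows. After Visit 4, new non-serious events lie outside the rule and new serious ones rely on passive reporting. For subjects who stop early, the gap concerns new events only.

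This rests on reading the last treatment visit as Visit 4, which the calendar and 9.11.1 support, and on day-counting from the nominal weeks. Absolute risk is low and the primary outcome is not affected. The benefit is individual safety and fuller ascertainment, largely retrospective for acute events; it is not rate estimation.

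**What to change.** In 9.11.2 and the Study Calendar, extend adverse-event and serious-adverse-event collection to one scheduled telephone contact about 2–3 weeks after each subject's own last dose. Name it as the final follow-up visit in item 3. Make it in both arms, which also protects the blind, and include early stoppers unless consent is withdrawn or the subject is lost to follow-up. Use the same non-directive questioning. How the drug is stopped does not change, and no clinic visit or test is added.

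Because a 3-week call can reach 93 days after long screening, either reword 4.5 to an approximate three months or call at 2 weeks when screening was long. State whether completion for the Section 12.2 reviews includes the call; if it does, those reviews move later by the same time.

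The cost is one calendar column, one sentence in 9.11.2, an IRB amendment, about 12 calls by existing staff (plus any replacements), and data closure about 2–3 weeks later.
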